AIM 2: To assess daily patterns of e-cigarette use (including dual use of combustible cigarettes), product satisfaction, and nicotine cravings with use of 4.5% vs 0 mg (placebo) e-cigarette; and

AIM 3: To compare the effect of nicotine e-cigarettes (4.5%) vs placebo e-cigarettes on smoking reduction at 1, 3 and 12 weeks post baseline assessment.

Study design

This pilot study will be a two-arm, randomized controlled trial. We will randomize 50 participants into each intervention arm. Participants will be recruited through advertisements placed in Craigslist and other social media as well as flyers placement in NYU venues and street distribution with contact details for how to get in touch with a Research Assistant. The randomization sequence will be prepared by the study statistician. Participants will be randomized to one of the two arms: e-cigarettes with nicotine cartridges or e-cigarettes with placebo cartridges (0mg). Participants and research assistants will be blind to the allocation of nicotine or placebo e-cigarettes as there are no difference in appearance or odor of the mist emitted from the e-cigarettes with and without nicotine containing cartridges.

Figure 1. Study design

Study participants

Inclusion criteria: ages 21-35 (must present proof of age), daily smoker, smokes at least 10 cigarettes a day (verified by a CO level of 8 ppm or above), interested in reducing CPDs, able to provide consent, uses a cell phone and is willing/ able to receive and respond to daily text messages regarding his/her cigarette use and e-cigarette use on his/her cell phone, and willing to use an e-cigarette for 3 weeks.

Exclusion criteria: Pregnant and/or breastfeeding (self-reported), current use of smoking cessation medications (including other forms of NRT, bupropion, or varenicline), enrolled in a smoking cessation program or another cessation trial. Other exclusion criteria include use of an e-cigarette in the past 14 days, use of any other tobacco products (pipe, cigar, cigarillos, snuff, chewing tobacco, or hookah/shisha) in the past 30 days, an Alcohol Use Disorders Identification Test (AUDIT C) score of ≥ 7

Name of study: Assessing the use of electronic cigarettes (e-cigarettes) as a harm reduction strategy

for men and ≥ 5 for women, a Drug Abuse Screening Test-10 (DAST) score of ≥ 5 . Potential participants will also be excluded if they report having a history of asthma or other airways disease and heart disease.

Study Procedures

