We will send questions via text messages for a total of 24 days (3 days of baseline assessment of cigarette use and 21 days of dual use with e-cigarette). The first phase of data collection will include a three-day baseline assessment of the study participants' usual smoking pattern. This will begin the day after the baseline assessment. Participants will receive text messages approximately every 4 hours (4 times/day). The questions will only ask about cigarette use in the previous time period, mood and cravings (Table 2). We will wait until the study participant responds to the first message before sending each follow up message. Depending on the participant's answer to whether or not they have smoked a cigarette and/or E-cigarette in the previous time period, they might receive different combinations of questions. For example, there are 6 questions in the first message each day for the 3 day baseline assessment of cigarette use. However if the participant has not smoked any cigarettes in the previous time period, they will only receive 3 of the questions. Each question is sent to the participant only after the previous one receives a response.

During the intervention stage which will last 3 weeks, we will again send text messages 4 x/day. These messages will assess the following 1) number of cigarettes smoked in the previous time period, 2) use of e-cigarettes, 3) satisfaction with cigarettes and/or e-cigarette ("On a scale of 0-9 how pleasurable was the last [cigarette/E-cigarettes]?"), and 4) cravings ("On a scale from 0-9 how much do you want to smoke a CIGARETTE right now?"). The first text of the day will also ask how soon after waking participants smoked a cigarette and used an e-cigarette and if they used cigarettes, how much do they want to smoke fewer cigarettes than usual and how hard it would be to use E-cigs only. Questions about use of e-cigarettes will include the following: 1) how many separate times in the previous time period did you use your e-cigarette ("time" is defined as around 5 or more puffs or 5 or more minutes of use), 2) On average, how many puffs did you take with each use, and 3) How many minutes ago was your last E-cigarette puff? We will use numerical scales because our experience has demonstrated that this allows for more accurate data collection.

If subjects do not return any messages for a 24 hour period we will contact them by phone to assess if there is a problem with receiving the texts.

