
All measures collected during study visits and by telephone at 12 weeks, will be summarized for each time point with standard descriptive statistics and frequency tables, as appropriate. Measures with significant baseline treatment group differences (assessed by analysis of variance or chi-squared as appropriate to the primary outcome measure) will be considered for inclusion as covariates in a generalized linear mixed model analysis.

In terms of the EMA data, as per Shiffman (2013), analysis of the EMA data will be handled through several different approaches depending on the research question. For example, if we want to assess differences between individuals with no reference to change over time we can ask if there is a correlation between cravings and e-cigarette use. Data would be collapsed over time, averaging craving ratings for each subject from all signal-contingent assessments in order to derive a single

Name of study: Assessing the use of electronic cigarettes (e-cigarettes) as a harm reduction strategy

craving score. Using simple Pearson correlation across subjects we can assess correlations between cravings and e-cigarette use. If we are interested in assessing how craving intensity changes with changes in cigarette use we would use a GEE model (Shiffman 2013).

We will assess multiple aspects of intervention feasibility including the eligibility rate (the proportion of smokers who were eligible for trial participation), the acceptance rate (the percentage of eligible individuals we recruited to the study) and reasons for study ineligibility and refusal. We will compare retention rates in the two study arms at each study visit (weeks 1,3, and 12). We will also assess consistency in tracking use of e-cigarettes and cigarettes, and satisfaction with e-cigarettes (see measures section). We will compute frequencies and percentages for categorical outcomes and means, standard deviations, medians, and interquartile range for continuous outcomes. As part of our feasibility analysis, we will conduct qualitative interviews with 10 subjects in each arm at 1 and 3 weeks. Interview transcripts will be analyzed with Atlas.ti. A coding manual of core and secondary codes will be developed by [name] and [name], both experienced qualitative researchers. Intercoder reliability will be assessed by examining rates of disagreement.

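### The example given for relating craving to e-cigarette use has no term for randomised arm and, as a separate and smaller matter, averages craving over prompts sent before the product is supplied

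*Combined protocol and SAP*

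**What the plan says.** The Data Analysis and Data Monitoring section says that the text-message data will be analysed in different ways for different questions, and introduces one of them conditionally: "For example, if we want to assess differences between individuals with no reference to change over time we can ask" whether craving goes with e-cigarette use. The craving score comes from collapsing over time, "averaging craving ratings for each subject from all signal-contingent assessments". The analysis is then: "Using simple Pearson correlation across subjects we can assess correlations between cravings and e-cigarette use". No time window, arm term, stratification or partial correlation is mentioned.

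The Text message assessment section sets the period as "3 days of baseline assessment of cigarette use and 21 days of dual use with e-cigarette", with four prompts a day. Table 2 marks the craving item at all four daily prompts in both phases, but the item counting e-cigarette uses only in the intervention phase. Under Study Procedures, participants collect their e-cigarettes after the tracking days and the counselling session. Their only earlier contact with the study product is practice at the baseline visit.

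Aim 2 covers "product satisfaction, and nicotine cravings with use of 4.5% vs 0 mg (placebo) e-cigarette". The Secondary outcomes paragraph lists cravings and adds an exploratory comparison of outcomes between the arms. The Number of Subjects section gives 100 participants, 50 per arm.

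**The concern.** Arm is randomised and could plausibly affect both variables: nicotine content may change craving, and it may change how much the device is used. A correlation across all participants then mixes two things: the association among people using the same product, and the difference between the two products. It could be reported as a link between use and craving when it shows only nicotine against placebo. If the arm differences run in opposite directions, for example lower craving and more use with nicotine, it could also conceal a positive association present within each arm.

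The second issue is one of definition. A craving mean that takes in the tracking days covers a time when participants had no supply of the device, while the count of uses covers only the time when they had one.

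**Working it through.** **Stated figures.** The documents give no power, significance level or expected correlation for this analysis, so there is no figure to reproduce.

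**Share of prompts before supply.**
- Tracking: 3 × 4 = 12 prompts.
- Intervention: 21 × 4 = 84 prompts.
- Share: 12/96 = 12.5%, if every prompt is answered.

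**Effect of leaving out arm.** Take two equal arms. Let r_w be the within-arm correlation, and let d_c and d_u be the arm differences in craving and use, in within-arm SDs. Then

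r = (r_w + d_c·d_u/4) / √[(1 + d_c²/4)(1 + d_u²/4)].

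The gaps are assumptions, because the documents give none. The chance of significance uses the Fisher z approximation with N = 100 and an assumed two-sided 5% level (critical |r| = 0.197).

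With r_w = 0 and equal gaps:

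| Gap in both (SD) | \|r\| | Significant |
|---|---|---|
| 0.3 | 0.0225/1.0225 = 0.02 | 5.5% |
| 0.5 | 0.0625/1.0625 = 0.06 | 9% |
| 0.8 | 0.16/1.16 = 0.14 | 28% |
| 1.0 | 0.25/1.25 = 0.20 | 52% |

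The sign is positive when the gaps run the same way and negative when they are opposite.

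Because the bias depends on the product of the gaps, one large gap is not enough. Gaps of 0.8 and 0.2 SD give 0.04/√(1.16 × 1.01) = 0.04, significant about 6.5% of the time.

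Masking, with opposite gaps:
- A true r_w of 0.20 with 0.8 SD gaps becomes (0.20 − 0.16)/1.16 = 0.03.
- A true r_w of 0.30 with 1.0 SD gaps becomes (0.30 − 0.25)/1.25 = 0.04.
- Either is significant only 6–7% of the time.

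**Effect of the tracking-day prompts.** This was simulated with 4,000 replicates of 50 per arm. Craving was 0.125 × tracking + 0.875 × intervention, and the two were assumed to correlate 0.4 or 0.7.
- With opposite 1.0 SD gaps and r_w = 0, mean r moves from −0.20 without the tracking prompts to −0.19 or −0.18 with them.
- With no arm gap and r_w = 0.30, mean r is 0.30 either way.

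The early prompts therefore slightly weaken the arm-driven correlation. They do not create it.

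**Which change does the work.** With opposite 0.8 SD gaps and r_w = 0, restricting the window alone gives mean r = −0.14 (about 28% significant), against −0.13 (about 26%) with all prompts. Taking the correlation within arm, on intervention prompts, gives a mean of about 0.00 and about 5% significant. With gaps still present, a true r_w of 0.20 or 0.30 is recovered as about 0.20 or 0.30, significant in about 52% or 86% of replicates.

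**The case against.** The passage illustrates a type of analysis; it does not commit the trial to a test. It is conditional throughout, and no hypothesis, significance level or aim is tied to it. It never says that the arms are pooled without adjustment. The phrase about subjects most naturally contrasts between-person with within-person analysis, since a GEE for change over time follows. The cravings part of Aim 2 is served by the separate exploratory comparison of outcomes between arms, which this correlation does not replace. The larger error rates need large gaps in both variables. And a descriptive between-person correlation need not be read as a within-arm one.

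Most of this stands, and it limits the point. A reader might infer that the trial has fixed on a pooled analysis; the documents support only silence about arm in an example. A reader might infer that Aim 2's comparison of craving by arm is compromised; it is provided for elsewhere. A reader might also infer that the pre-supply prompts produce the spurious arm association; craving before supply cannot reflect the supplied product, and the calculation shows dilution.

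What remains is that no other text supplies the missing term. The mixed-model sentence concerns covariates with baseline imbalance, the GEE sentence concerns craving and cigarette use, and the comparison between arms answers a different question. The example is the only method given for craving and e-cigarette use, so it may well be followed as written.

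**Conclusion.** The point holds as a minor one with two independent parts.

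The omission of arm is the part that can mislead. The distortion is slight when the gaps in both variables are about 0.5 SD or less, or when either gap is small, and material when both are about 0.8 to 1.0 SD. Whether gaps of that size will occur cannot be known from the documents. The figures assume equal arms of 50, complete data, a two-sided 5% level, within-arm correlations of 0 to 0.30, and a within-arm association as the quantity of interest.

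The 12.5% of prompts sent before supply are a mismatch of periods, worth tidying but with little numerical effect.

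Because the analysis is exploratory and the trial is a pilot, neither part threatens the main conclusions.

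**What to change.** If this analysis is run, specify the following:

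- Compute both the craving mean and e-cigarette use from the 84 intervention-period prompts, and name the use variable (for example, number of separate uses).
- Make the partial correlation adjusted for arm the main estimate.
- Show the correlation in each arm descriptively. With n = 50 the standard error on the Fisher z scale is 1/√47 = 0.146, against 1/√96 = 0.102 for the arm-adjusted estimate, so the per-arm values are less precise.
- Optionally, add a sensitivity analysis that also adjusts for mean craving over the three tracking days.
- If an unadjusted pooled correlation is shown, label it as not separating arm from use.

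The cost is a sentence or two in the analysis section, a small change in code and one degree of freedom. All the data are already collected.

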Table 2. Text messages and schedule

Rule (based on answer to the first question)	Text	3 days baseline tracking cig use				Intervention period			
		1 st	2 nd	3 rd	4 th	1 st	2 nd	3 rd	4 th
	Since your last report: Did you smoke a cigarette and/or E-cigarette? [no=0; cig=1; Ecig=2; both=3]	X	X	X	X	X	X	X	X
	Thinking about this morning, how many minutes after waking did you smoke your first cigarette? (Text 9999 if you did not smoke any cigarettes today)				X				X
	Thinking about this morning, how many minutes after waking did you use your first E-cig? (Text 9999 if you did not use any E-cigs today)								X
	Thinking about TODAY only: Do you want to smoke fewer cigarettes than usual? [0=Not at all ; 9=Very, Very Much]					X			
	Thinking about TODAY only: How hard would it be to use E-cigs ONLY? [0=Not at all ; 9=Extremely]					X			
If used cig	Since your last report: How many cigarettes did you smoked?	X	X	X	X	X	X	X	X
If used cig	How many minutes ago did you smoke a cigarette? [Text "0" if your are currently smoking]	X	X	X	X	X	X	X	X
If used cig only	On a scale of 0-9 how satisfying was your last cigarette? [0=Not at all – 9=Extremely Satisfying]	X	X	X	X	X	X	X	X
If used e-cig	Since your last report: How many separate times did you use an E-cigarette?					X	X	X	X
If used e-cig only	On average, how many puffs did you take with each use?					X	X	X	X
If used e-cig	How many minutes ago was your last E-cigarette puff? [Text "0" if you are currently using an E-cigarette]					X	X	X	X
If used e-cig	On a scale of 0-9 how satisfying was your last E-cigarette? [0=Not at all – 9=Extremely Satisfying]					X	X	X	X
	On a scale of 0-9, how much do you want to smoke a CIGARETTE right now? [0=Not at all – 9=Very, Very much]	X	X	X	X	X	X	X	X
	Thank you for completing the survey.	X	X	X	X	X	X	X	X

Primary outcome: For Aim 3, the primary outcome will be reduction in CPD and we will summarize this data as the proportion of participants who achieve 50% reduction in CPD at 3 weeks. Smoking reduction will be measured by a combination of self-report, text message data and changes in CO and saliva cotinine between baseline and end of treatment (3 weeks).

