Secondary outcomes: We will assess potential side effects associated with e-cigarette use, additional use of other tobacco products and/or marijuana, satisfaction with the e-cigarettes, nicotine urges/cravings and withdrawal symptoms. An exploratory secondary aim includes assessing differences in the primary and secondary outcomes between the intervention arms.

Name of study: Assessing the use of electronic cigarettes (e-cigarettes) as a harm reduction strategy

Feasibility measures include: 1) Percentage of subjects screened who are eligible and enroll, 2) percentage retained at 3 and 12 weeks, 3) retention across study conditions, 4) consistency in tracking use of e-cigarettes and cigarettes, and 5) satisfaction with e-cigarettes.

Characteristics of the Research Population

Described above under the study participants section.

Number of Subjects

We expect to enroll 100 smokers total, 50 in each arm.

Gender of Subjects

We would ensure equitable inclusion of both men and women in this study.

Age of Subjects

All subjects will be 21-35. We are particularly interested in studying the effectiveness of e-cigarettes as a harm reduction strategy among young adults as this is an understudied population and one that has demonstrated exceptionally high rates of adoption of this product.

Racial and Ethnic Origin

We will recruit across all racial and ethnic groups.

Inclusion Criteria

All subjects must be between 21-35 years old, daily smokers, smoke at least 10 cigarettes per day, interested in reducing CPDs, able to provide consent, use a cell phone, are willing/able to receive and respond to daily text messages regarding their cigarette use and e-cigarette use on their cell phone, and are willing to use an e-cigarette for 3 weeks.

Exclusion Criteria

Subjects will be excluded if they are pregnant and/or breast feeding (self-reported), are currently using smoking cessation medications (including other forms of NRT, bupropion, or varenicline), are enrolled in a smoking cessation program or another cessation trial, have used an e-cigarette in the past 14 days, have used any other tobacco products (pipe, cigar, cigarillos, snuff, chewing tobacco, rolling tobacco, or hookah/shisha) in the past 30 days, score ≥ 7 (men) or ≥ 5 (women) on the Alcohol Use Disorders Identification Test (AUDIT-C), score ≥ 5 on the Drug Abuse Screening Test-10 (DAST), or report having a history of asthma, other airways diseases, or heart disease.

Data Analysis and Data Monitoring

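### The GEE for craving against cigarette use has no step separating within-person change from between-person differences, so a single cigarette term would blend the two

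*Combined protocol and SAP*

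**What the plan says.** The section on data analysis and data monitoring in the combined protocol and SAP says that "analysis of the EMA data will be handled through several different approaches depending on the research question", and then gives two examples.

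- The first applies "if we want to assess differences between individuals with no reference to change over time". Craving is averaged over time for each participant and correlated with e-cigarette use across participants by a Pearson coefficient.
- The second is the one at issue: "If we are interested in assessing how craving intensity changes with changes in cigarette use we would use a GEE model". A methods paper is cited and nothing else is specified: no form for the cigarette predictor, no participant-mean term, and no working correlation, lag, time term or arm term.

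The data come from the text-message assessment: "We will send questions via text messages for a total of 24 days", of which 3 are baseline tracking and 21 are intervention days, with four prompts a day. Each intervention prompt covers the "number of cigarettes smoked in the previous time period", and the craving item in Table 2 reads "On a scale of 0-9, how much do you want to smoke a CIGARETTE right now", scored 0 to 9. On sample size the plan states: "We expect to enroll 100 smokers total, 50 in each arm".

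**The concern.** By setting the second question against one about differences between people, the plan makes it a question about change: when a given participant smokes more or less, does that participant's craving move? The cigarette count varies at both levels. Participants differ in how much they smoke, because entry requires at least 10 a day with no upper limit. Each participant's own count should also move, because everyone is encouraged to cut to half of baseline or below.

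A GEE allows for correlation among a person's repeated ratings. It does not by itself isolate the within-person slope. With one cigarette term, heavier smokers craving more (a between-person fact) can be reported as craving rising and falling with a person's own smoking. Craving appears in Aim 2 and among the secondary outcomes, and participants are asked to substitute e-cigarettes to limit withdrawal symptoms. A positive blended slope could therefore be misread as evidence that cutting down lowers craving.

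**Working it through.** The plan gives no effect size, power or variance figure for this analysis, so there is nothing of its own to reproduce.

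**Inputs from the documents.** 100 participants; (3 + 21) days × 4 prompts = 96 prompts each, 9,600 in all; craving 0 to 9; a cigarette count at each prompt.

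**Assumed inputs.** Between-person slope bB = +0.5; within-person slope bW = -0.10, 0 or -0.30; ICC (the share of cigarette-count variance lying between people) 0.1 to 0.7; residual craving ICC 0.1 and 0.3; working correlation ρ from 0 to 0.5; answered prompts m = 8, 24 or 96.

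**Step 1: one term, independence.** The coefficient is about ICC × bB + (1 - ICC) × bW.

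- ICC 0.25, bW = -0.10: 0.25 × 0.5 + 0.75 × (-0.10) = 0.125 - 0.075 = +0.05, the wrong sign. A simulation of 100 people with 84 intervention prompts (21 × 4) gave 0.051.
- ICC 0.25, bW = 0: 0.125, an apparent association where none exists within people. The simulation gave 0.127, with SE about 0.04.
- The sign reverses when ICC exceeds -bW / (bB - bW): 0.10/0.60 = 0.17 for bW = -0.10, and 0.30/0.80 = 0.375 for bW = -0.30.

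**Step 2: dependence on the working correlation.** Under an exchangeable structure the between-person sum of squares is weighted by (1 - ρ)/(1 + (m - 1)ρ) relative to the within-person one. Results for bB = +0.5, bW = -0.30, 96 prompts:

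| ICC | Independence (formula) | AR(1) (simulated) | Exchangeable (simulated) |
|---|---|---|---|
| 0.2 | -0.14 | -0.19 to -0.23 | -0.294 to -0.295 |
| 0.3 | -0.06 | -0.13 to -0.20 | -0.293 |
| 0.5 | +0.10 | +0.01 to -0.12 | -0.278 to -0.292 |
| 0.7 | +0.26 | +0.20 to +0.07 | -0.267 to -0.285 |

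Ranges cover residual craving ICC 0.1 to 0.3, with 15 replicates per setting. The largest exchangeable bias is 0.300 - 0.267 = 0.033. With bW = -0.10 and ICC 0.25, exchangeable gave -0.094.

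**Step 3: few answered prompts.** With ICC 0.7 and ρ fixed at 0.1, the exchangeable formula gives +0.02 at 24 prompts and +0.15 at 8. These are unfavourable cases. In practice ρ is estimated from residuals that contain the between-person misfit, which raises it and shrinks the bias. For example, in the 96-prompt setting with ICC 0.7 and residual craving ICC 0.1, the between-person residual variance is about 0.1 + 0.7 × (0.5 + 0.267)² = 0.51. That makes ρ about 0.51/(0.51 + 0.90) = 0.36, not 0.1.

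**Step 4: two terms.** With the participant mean and the deviation entered separately, the within-person estimate was -0.296 to -0.304 in every simulated setting, even under independence. In the ICC 0.25 simulation it was -0.096 (true -0.10) and 0.004 (true 0), with SE 0.009 against 0.044 for the single term under independence.

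**The case against.** The strongest reply is that the plan never says raw counts will enter as a single term. The predictor it names is change in cigarette use, it has already sent the between-person question to another method, and a GEE can carry a mean and a deviation term. This stands: the plan has a gap in specification, not a declared wrong model, and choosing a GEE is not itself an error.

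Reading the predictor as change from the three-day baseline does not close the gap, because participants who cut down a lot and those who cut down little still differ on average. Prompt-to-prompt differences would remove most of the between-person part, but the plan does not specify them.

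The size also depends on assumed inputs. With ICC 0.25 and a between-person slope of +0.20, independence gives 0.05 - 0.075 = -0.025 for a true -0.10, which is the correct sign. For a true slope of 0 it gives 0.05, against an SE of about 0.04. Exchangeable correlation with near-complete data leaves little bias. All of this stands.

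Finally, the model is offered as an example in a pilot. It is not the primary outcome, and it cannot guide the trial's own counselling, which takes place before e-cigarettes are supplied. That limits the weight of the point but does not remove it.

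**Conclusion.** The plan poses a within-person question and gives no step that isolates within-person change. With a single cigarette term, whether raw count or change from baseline, the answer would depend on an unstated working correlation. It could range from nearly unbiased (exchangeable, near-complete data) to wrong in sign (independence above ICC 0.17 or 0.375 in the two cases worked; AR(1) at ICC 0.5 to 0.7 in some settings). These sizes rest on assumed slopes and variance shares, and there is no bias if the two slopes are equal.

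A reader might infer that the planned analysis will give a wrong-signed result. The documents do not support that: it would need a single blended term, an unfavourable working correlation and a sizeable gap between the slopes, none of which they state. Nor does the point reach the primary outcome, a 50% reduction in cigarettes per day at 3 weeks.

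**What to change.** In the data analysis section, replace the bare reference to a GEE with a stated model for craving at each prompt. Its terms would be:

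- the participant's own mean cigarettes per prompt;
- that prompt's deviation from the mean;
- study arm;
- study phase or time, distinguishing the 3 baseline days from the intervention days.

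Use robust standard errors, and name the working correlation and any lag between smoking and craving. Report the deviation term as the within-person association and the mean term as the between-person one.

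Do not present the deviation term as the causal effect of cutting down. E-cigarettes are supplied just as participants are asked to reduce, so reduction, substitution and study phase move together, and the added terms do not fully separate them.

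The cost is one derived variable and a few model terms, all from data already being collected.
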